### 6.5.1.1.3 Immune-Related Adverse Events and Cytokine-Mediated Toxicity: Monitoring and Management

Management algorithms for immune-related AEs (irAEs, which are also referred to as immune-mediated AEs [imAEs] in this document) are provided in Section 6.5.2.1.2.

Cytokine-release syndrome (CRS) is a clinical diagnosis presenting usually with a constellation of symptoms often characterized by but not limited to, persistent fever, hypotension, dyspnea associated with or without tachypnea, headache, tachycardia, and rash caused by the release of cytokines. End organ dysfunction with varied manifestation can be seen in CRS as well. Many of these symptoms overlap with known AEs seen in bempegaldesleukin and checkpoint inhibitors combination therapy (ie, pyrexia and hypotension). These symptoms may be seen in infusion reactions as well as other known syndromes, such as tumor lysis syndrome and macrophage activation syndrome. Note:

- For suspected, serious AE of CRS of Grade  $\geq 3$ , the Investigator is required to contact the Sponsor.
- For patients in Arm A receiving bempegaldesleukin: an algorithm for the management of CRS is provided [Appendix 6](#).

### 6.5.1.1.4 Monitoring and Management of Bempegaldesleukin-Induced Eosinophilia for Patients in Arm A Receiving Bempegaldesleukin:

Frequent and significant eosinophilia has been observed in patients receiving bempegaldesleukin, primarily starting at Cycle 2 or later, consistent with the known biological effect of IL-2 therapy. Clinical data analysis demonstrated that frequency of selected AEs (primarily Grade 1 or 2 in severity) such as rash, pruritus, edema, nausea, vomiting, diarrhea, and dizziness increased with level of eosinophilia. Isolated cases of hypereosinophilic syndrome and other eosinophilic disorders have been reported.

For patients in Arm A receiving bempegaldesleukin: absolute eosinophil count should be closely monitored per protocol. If a study patient is suspected to have eosinophilic disorder (symptoms may involve skin, lungs, digestive tract, heart, blood, or nervous systems) with absolute eosinophil count at or above 5000/ $\mu\text{L}$  ( $5 \times 10^9/\text{L}$ ) level, bempegaldesleukin treatment may need to be withheld, and the patient should be treated as clinically indicated ([Table 4](#)).

**Table 4: Management of Bempegaldesleukin-Induced Eosinophilia For Patients in Arm A Receiving Bempegaldesleukin**

Event		Clinical Management
Absolute Eosinophil Value	Symptomatic? a	
$\geq 5000/\mu\text{L}$ ( $5 \times 10^9/\text{L}$ )	Yes	Bempegaldesleukin may need to be withheld; treat patient symptoms as clinically indicated.

a. Symptoms may involve skin, lungs, digestive tract, heart, blood, and nervous systems.

### 6.5.1.2 Bempegaldesleukin Dose Delay and Reduction Criteria

Dose delays and one dose reduction are permitted for bempegaldesleukin. Bempegaldesleukin may be delayed or reduced to 0.003 mg/kg based on observed drug-related toxicities. Medical Monitor consultation is required for dose reduction. For patients who have a dose reduction to 0.003 mg/kg: if the toxicity requiring dose reduction has resolved, bempegaldesleukin 0.006 mg/kg may be reinstated after a careful risk assessment.

Bempegaldesleukin may be delayed or reduced for the following reasons:

- For infusion reactions, refer to Section 6.5.2.1.1.
- For irAEs, refer to Section 6.5.2.1.2.
- Grade  $\geq 2$  creatinine increase:
  - For patients who must delay study treatment due to Grade  $\geq 2$  creatinine increase due to a non-inflammatory cause, delay retreatment with study drug for approximately 3 to 5 days. After the dosing delay, the patient may resume study drug when serum creatinine has returned to Grade  $\leq 1$ , as assessed within 24 hours prior to redosing (or as soon as locally feasible, except where permanent discontinuation of study drug is required [see Section 6.5.1.3]).
- Grade  $\geq 3$  toxicity at least possibly related to bempegaldesleukin: bempegaldesleukin must be delayed until resolution to Grade 1 or baseline (unless otherwise requiring permanent discontinuation per Section 6.5.1.3), patients with the following laboratory values can continue study drug:
  - Grade  $\geq 3$  lymphopenia
  - Grade  $\geq 3$  asymptomatic amylase or lipase elevation
- Patient has acute infection (eg, fever, upper or lower respiratory tract infection) requiring systemic antibiotic therapy. Patient may resume study treatment once free of signs or symptoms for 72 hours after completion of antibiotic therapy.
- For eosinophilia, refer to Section 6.5.1.1.4.
- Any AE, laboratory abnormality, or intercurrent illness which, in the judgment of the Investigator, warrants delaying the dose of study medication.

Bempegaldesleukin dosing may resume at the same bempegaldesleukin dose or at the lower bempegaldesleukin dose level when toxicity resolves to Grade  $\leq 1$  or returns to baseline, except for instances where the potential recurrence of the event poses an undue risk for the patient.

### 6.5.1.3 Bempegaldesleukin Discontinuation Criteria

For toxicities requiring discontinuation of treatment with bempegaldesleukin, pembrolizumab alone may continue as a monotherapy if the toxicity is considered by the Investigator to be not related to pembrolizumab.

For CVA events and suspected TIA events, follow the criteria described below (additional details are provided in the CVA management algorithm in [Appendix 2](#)).

Bempegaldesleukin treatment should be permanently discontinued for the following:

- For infusion reactions, in accordance with the criteria in Section [6.5.2.1.1](#).
- For irAEs, in accordance with the criteria in Section [6.5.2.1.2](#).
- For any Grade 4 drug-related AE or clinically significant laboratory abnormality, with the exception of the following events, which do not require discontinuation:
  - Grade 4 neutropenia  $\leq$  7 days.
  - Grade 4 lymphopenia or leukopenia  $\leq$  14 days in duration.
  - Isolated Grade 4 amylase or lipase abnormalities that are not associated with symptoms or clinical manifestations of pancreatitis and decrease to Grade  $<$  4 or return to baseline within 7 days.
  - Isolated Grade 4 electrolyte imbalances/abnormalities that are not associated with clinical sequelae and are corrected with supplementation/appropriate management within 72 hours of their onset.
- Any AE, laboratory abnormality, or intercurrent illness that, in the judgment of the Investigator, presents a substantial clinical risk to the patient with continued treatment.
- Any new CVA event confirmed by imaging (diffusion-weighted imaging [DWI] MRI preferred unless otherwise contraindicated) regardless of neurological symptoms (eg, cryptogenic CVA) and for a suspected TIA event without clear alternative etiology (see [Appendix 2](#)).

Tumor assessments should continue as per protocol even if dosing is delayed, and patients must otherwise meet the criteria for continued treatment at the time re-initiation of study therapy is considered.

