### 6.5.2.1.2 Immune-related AEs Associated with Pembrolizumab

AEs associated with pembrolizumab exposure may represent an immune-related response. These irAEs may occur shortly after the first dose or several months after the last dose of pembrolizumab treatment and may affect more than one body system simultaneously. Therefore, early recognition and initiation of treatment is critical to reduce complications. Based on existing clinical study data, most irAEs were reversible and could be managed with interruptions of pembrolizumab, administration of corticosteroids and/or other supportive care. For suspected irAEs, ensure adequate evaluation to confirm etiology or exclude other causes. Additional procedures or tests such as bronchoscopy, endoscopy, skin biopsy may be included as part of the evaluation.

Dose modification and toxicity management guidelines for irAEs associated with pembrolizumab are provided in [Table 6](#). These guidelines apply to patients **receiving bempegaldesleukin in combination with pembrolizumab OR either treatment as a monotherapy**.

For toxicities requiring treatment discontinuation, bempegaldesleukin or pembrolizumab alone may continue as a monotherapy if the toxicity is considered not related to that study drug by the Investigator.

**For patients in Arm A receiving bempegaldesleukin**, elevations of AST or ALT occurring in Cycle 1 should be managed according to the guidelines in Section [6.5.1.1.2](#). For elevations of AST or ALT occurring in Cycle 2 or beyond, follow the dose modification and toxicity management guidelines in [Table 6](#).

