	Recurrent Grade 3 or Grade 4	Permanently discontinue		
AST or ALT elevation or Increased Bilirubin f	Grade 2 a	Withhold	
 
Administer corticosteroids (initial dose of 0.5 - 1 mg/kg prednisone or equivalent) followed by taper
 
	
 
Monitor with liver function tests (consider weekly or more frequently until liver enzyme value returned to baseline or is stable)
 

	Grade 3 b or 4 c	Permanently discontinue	
 
Administer corticosteroids (initial dose of 1 - 2 mg/kg prednisone or equivalent) followed by taper
 
	
Type 1 diabetes mellitus (T1DM) or Hyperglycemia	New onset T1DM or Grade 3 or 4 hyperglycemia associated with evidence of b-cell failure	Withhold d	
 
Initiate insulin replacement therapy for patients with T1DM
 
Administer anti-hyperglycemic in patients with hyperglycemia
 
	
 
Monitor patients for hyperglycemia or other signs and symptoms of diabetes
 

Hypophysitis	Grade 2	Withhold	
 
Administer corticosteroids and initiate hormonal replacements as clinically indicated
 
	
 
Monitor for signs and symptoms of hypophysitis (including hypopituitarism and adrenal insufficiency)
 

	Grade 3 or 4	Withhold or permanently discontinue d		

irAEs	Toxicity Grade (CTCAE v5.0)	Action with Study Treatment	Corticosteroid and/or Other Therapies	Monitoring and Follow-Up
Hyperthyroidism	Grade 2	Continue	
 
Treat with non-selective beta-blockers (eg, propranolol) or thionamides as appropriate
 
	
 
Monitor for signs and symptoms of thyroid disorders
 

	Grade 3 or 4	Withhold or permanently discontinue d		
Hypothyroidism	Grade 2, 3, 4	Continue	
 
Initiate thyroid replacement hormones (eg, levothyroxine or liothyronine) per standard of care
 
	
 
Monitor for signs and symptoms of thyroid disorders
 

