**Note: Non-irAE will be managed as appropriate, following clinical practice recommendations.**

- a. AST/ALT:  $> 3.0 - 5.0 \times \text{ULN}$  if baseline normal;  $> 3.0 - 5.0 \times \text{baseline}$ , if baseline abnormal;  
bilirubin:  $> 1.5 - 3.0 \times \text{ULN}$  if baseline normal;  $> 1.5 - 3.0 \times \text{baseline}$  if baseline abnormal
- b. AST/ALT:  $> 5.0$  to  $20.0 \times \text{ULN}$ , if baseline normal;  $> 5.0 - 20.0 \times \text{baseline}$ , if baseline abnormal;  
bilirubin:  $> 3.0 - 10.0 \times \text{ULN}$  if baseline normal;  $> 3.0 - 10.0 \times \text{baseline}$  if baseline abnormal
- c. AST/ALT:  $> 20.0 \times \text{ULN}$ , if baseline normal;  $> 20.0 \times \text{baseline}$ , if baseline abnormal;  
bilirubin:  $> 10.0 \times \text{ULN}$  if baseline normal;  $> 10.0 \times \text{baseline}$  if baseline abnormal
- d. The decision to withhold or permanently discontinue study treatment is at the discretion of the investigator or treating physician. If control achieved or  $\leq$  Grade 2, study treatment may be resumed.
- e. Events that require discontinuation include but are not limited to: encephalitis and other clinically important irAEs (eg, vasculitis, sclerosing cholangitis).
- f. For patients in Arm A receiving bempegaldesleukin in Cycle 1, consult the guidelines in Section [6.5.1.1.2](#).

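### For Arm A, Section 6.5.1.3 requires permanent discontinuation of bempegaldesleukin at related Grade 4 hypothyroidism, Table 6 says continue, and no precedence is stated; other endocrine rows conflict in part

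*Protocol*

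**What the plan says.** Section 6.5.1.3 opens with "Bempegaldesleukin treatment should be permanently discontinued for the following" and then lists parallel bullets. One covers immune-related events: "For irAEs, in accordance with the criteria in Section" 6.5.2.1.2, which contains Table 6. The next reads "For any Grade 4 drug-related AE or clinically significant laboratory abnormality, with the exception of the following events, which do not require discontinuation". The exceptions are short-lived neutropenia, short-lived lymphopenia or leukopenia, isolated amylase or lipase abnormalities, and, last, "Isolated Grade 4 electrolyte imbalances/abnormalities that are not associated with clinical sequelae" that are promptly corrected.

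Section 6.5.1.2 has a similar pair of bullets. One refers immune-related events to Section 6.5.2.1.2. Another, for Grade 3 or higher, covers "toxicity at least possibly related to bempegaldesleukin: bempegaldesleukin must be delayed until resolution to Grade 1 or baseline" and exempts only lymphopenia and asymptomatic amylase or lipase elevation.

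Section 6.5.2.1.2 says that Table 6 applies to patients "receiving bempegaldesleukin in combination with pembrolizumab OR either treatment as a monotherapy". Its endocrine rows are:

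- Hypothyroidism, Grade 2, 3 or 4: Continue, with the instruction "Initiate thyroid replacement hormones (eg, levothyroxine or liothyronine) per standard of care".
- New-onset type 1 diabetes, or Grade 3 or 4 hyperglycemia with beta-cell failure: Withhold, with footnote d.
- Hypophysitis and hyperthyroidism, Grade 3 or 4: withhold or permanently discontinue, with footnote d.

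Footnote d states: "The decision to withhold or permanently discontinue study treatment is at the discretion of the investigator or treating physician". It also lets treatment resume once control is achieved or the event is at Grade 2 or below.

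**The concern.** An endocrine event in Arm A can be both a Table 6 immune-related event and a bempegaldesleukin-related event, so both sets of rules reach it. Thyroid dysfunction is an identified risk of bempegaldesleukin (Section 2.2.1), and Section 10.4 suggests attributing an event to both drugs when the evidence does not separate them.

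For such an event at Grade 4, a site reading the Grade 4 bullet stops the experimental drug for good. A site reading the hypothyroidism row of Table 6 keeps dosing. Patient management, bempegaldesleukin exposure and the count of discontinuations due to adverse events would then depend on which page the site consulted, across about 225 planned sites. Arm B is not exposed to this, because Sections 6.5.1.2 and 6.5.1.3 concern bempegaldesleukin only.

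**Working it through.** No figure in the plan bears on this point, so the check is a comparison of texts for an Arm A event judged related to bempegaldesleukin.

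| Event | Section 6.5.1.3 (Grade 4) or 6.5.1.2 (Grade 3) | Table 6 | Can both be followed? |
|---|---|---|---|
| Grade 4 hypothyroidism | Permanent stop | Continue | No |
| Grade 4 hyperglycemia / type 1 diabetes | Permanent stop | Withhold; footnote d | Only if the investigator uses the discretion to discontinue |
| Grade 4 hypophysitis or hyperthyroidism | Permanent stop | Withhold or discontinue; footnote d | Only if the investigator chooses to discontinue |
| Grade 3 hypothyroidism | Delay to Grade 1 or baseline | Continue | No, but what differs is a delay |
| Grade 3 hyperglycemia / type 1 diabetes, hypophysitis, hyperthyroidism | Delay to Grade 1 or baseline | Withhold (or discontinue); may resume when controlled or at Grade 2 or below | Yes, if the site waits for Grade 1 or baseline |

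**Is the disagreement wider than the endocrine rows?** At Grade 4, the rows for pneumonitis, diarrhea/colitis, liver tests, nephritis, neurological toxicity, myocarditis and all other immune-related events require permanent discontinuation, in line with Section 6.5.1.3. Among the rows that assign an action to Grade 4, only the endocrine ones depart from it.

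**Is precedence stated anywhere?** Section 6.5.1.3 lists the immune-related bullet and the Grade 4 bullet side by side and ranks neither. Section 6.5.2.1.2 gives the scope of Table 6 but does not say that it overrides Section 6.5.1.3. Section 6.6 makes the stopping criteria of both Section 6.5.1.3 and Section 6.5.2.1 binding, again without an order. The protocol does set boundaries elsewhere: Cycle 1 transaminase elevations go to Section 6.5.1.1.2 and later ones to Table 6; the Grade 3 rule in Section 6.5.1.2 yields expressly to Section 6.5.1.3; and the creatinine instruction is limited to non-inflammatory causes. The Grade 4 bullet carries no such limit.

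**Can one event meet both conditions?** For thyroid events, yes. Section 2.1.3.2.1 reports one hypothyroidism event on bempegaldesleukin alone, and Section 2.2.3 describes thyroid dysfunction consistent with an immune mechanism in patients given bempegaldesleukin with nivolumab. For hyperglycemia and hypophysitis the link rests mainly on the attribution guidance in Section 10.4.

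**How many patients?** The only related rate is in Section 2.2.2: 8.5% hypothyroidism on pembrolizumab monotherapy. Applied to 250 patients this gives 0.085 × 250 = 21.25, but it is an overall incidence, and the same paragraph says that most such events are mild to moderate. It does not estimate Grade 3 or Grade 4 events. For scale only, each percentage point of Arm A is 0.01 × 250 = 2.5 patients.

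**The case against.** The best reply is that the text can be harmonised. In both Section 6.5.1.2 and Section 6.5.1.3 the immune-related bullet comes before the general Grade 3 or Grade 4 bullet, Table 6 is a complete scheme with its own Grade 4 actions and a catch-all row, and Section 10.11 treats immune-mediated events as a distinct class. On that reading Table 6 governs immune-related events and the Grade 4 bullet covers everything else. The reading is plausible and may be what was intended, but it is not written: the Grade 4 bullet covers any drug-related event, and its exceptions omit endocrine events.

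Three other replies stand and limit the point.

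- A reader might infer that Table 6 says continue or withhold for every severe endocrine event, so that all of these rows contradict Section 6.5.1.3 outright. They do not. Table 6 itself offers discontinuation for hypophysitis and hyperthyroidism, and footnote d extends the choice to type 1 diabetes and hyperglycemia.
- A reader might infer an equal conflict at Grade 3. There the difference is a delay, and general instruction 4 of Table 6 (resume at Grade 1 or below) broadly agrees with Section 6.5.1.2. What remains is Grade 3 hypothyroidism and the threshold in footnote d.
- A reader might take the 21 patients above as the number affected, or count a loss of up to 34 cycles (35 − 1) per patient. The first figure covers all grades. The second is a ceiling that needs a Cycle 1 event in a patient who would otherwise have received all 35 cycles.

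Stopping bempegaldesleukin also need not end study treatment, since pembrolizumab may continue if the toxicity is judged unrelated to it. Finally, the SAP reports that the trial was discontinued with one patient enrolled and treated and that only listings will be produced, so no comparison of discontinuations between arms is at risk.

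**Conclusion.** The inconsistency is real and narrow. For related Grade 4 hypothyroidism in Arm A, Section 6.5.1.3 and Table 6 give mutually exclusive instructions. For the other three endocrine conditions at Grade 4, a mandatory stop meets a discretionary choice with resumption allowed. At Grade 3 there is a lesser mismatch over whether to delay (hypothyroidism) and when to resume (footnote d).

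This rests on two readings: that the bullets in Section 6.5.1.3 are parallel triggers, as they are laid out, and that an endocrine immune-related event can be judged related to bempegaldesleukin, which the protocol's own safety sections support for thyroid events. Its size cannot be computed from the documents. The number of patients is unknown and likely small, and with one patient treated the practical effect in this trial is limited. The contradiction still matters for patient safety in the protocol as written and in any text reused from it. No view is taken here on which clinical rule is right.

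**What to change.** Reconcile Section 6.5.1.2, Section 6.5.1.3, the endocrine rows of Table 6 and footnote d:

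1. State in both sections which one governs when an event is both an immune-related event listed in Table 6 and a Grade 3 or Grade 4 bempegaldesleukin-related adverse event.
2. Make the exception lists in Sections 6.5.1.2 and 6.5.1.3, the four endocrine conditions in Table 6 and the resumption threshold in footnote d agree with that statement.

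The sponsor's medical team decides which rule is kept. The cost is one precedence statement in each section and aligned lists, made if the protocol is amended or its text is reused. No patients, procedures or analyses are added.

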## **6.5.2 Pembrolizumab**

### **6.5.2.1 Dose Modification (Withhold, Treat, Discontinue) and Toxicity Management for Specific Adverse Events**

#### **6.5.2.1.1 Infusion Reactions**

Pembrolizumab may cause severe or life-threatening infusion reactions including severe hypersensitivity or anaphylaxis. Signs and symptoms usually develop during or shortly after drug infusion and generally resolve completely within 24 hours of completion of infusion. Dose modification and toxicity management guidelines on pembrolizumab-associated infusion reactions are provided in [Table 5](#).

These guidelines apply to patients receiving **bempegaldesleukin in combination with pembrolizumab OR either pembrolizumab or bempegaldesleukin treatment as a**

**monotherapy.** For toxicities requiring treatment discontinuation, bempegaldesleukin or pembrolizumab alone may continue as a monotherapy if the toxicity is considered not related to that study drug by the Investigator.

**Table 5: Infusion Reaction Dose Modification and Treatment Guidelines**

NCI CTCAE Grade	Treatment	Premedication at Subsequent Dosing

Grade 1
 
Mild reaction; infusion interruption not indicated; intervention not indicated
	
Increase monitoring of vital signs as medically indicated until the patient is deemed medically stable in the opinion of the Investigator.
	
Pembrolizumab monotherapy: None
 
Bempegaldesleukin alone or in combination with pembrolizumab:
 
Patient may be premedicated 1.5 hours (<math>\pm</math> 30 minutes) prior to infusion of study intervention with:
 
 
• Diphenhydramine 50 mg PO (or equivalent dose of antihistamine).
 
• Acetaminophen 500-1000 mg PO (or equivalent dose of analgesic).
 

Grade 2
 
Requires therapy or infusion interruption but responds promptly to symptomatic treatment (eg, antihistamines, NSAIDs, narcotics, IV fluids); prophylactic medications indicated for <math>\leq</math> 24 hours
	
Stop Infusion.
 
Additional appropriate medical therapy may include but is not limited to:
 
 
• IV fluids
 
• Antihistamines
 
• NSAIDs
 
• Acetaminophen
 
• Narcotics
 
 
Increase monitoring of vital signs as medically indicated until the patient is deemed medically stable in the opinion of the Investigator.
 
If symptoms resolve within 1 hour of stopping drug infusion, the infusion may be restarted at 50% of the original infusion rate (eg, from 100 mL/hr to 50 mL/hr). Otherwise dosing will be held until symptoms resolve and the patient should be premedicated for the next scheduled dose.
 
Patients who develop Grade 2 toxicity despite adequate premedication should be permanently discontinued from further study drug intervention.
	
Patient may be premedicated 1.5 hours (<math>\pm</math> 30 minutes) prior to infusion of study intervention with:
 
 
• Diphenhydramine 50 mg PO (or equivalent dose of antihistamine).
 
• Acetaminophen 500-1000 mg PO (or equivalent dose of analgesic).
 

NCI CTCAE Grade	Treatment	Premedication at Subsequent Dosing

Grades 3 or 4
 
Grade 3: Prolonged (ie, not rapidly responsive to symptomatic medication and/or brief interruption of infusion); recurrence of symptoms following initial improvement; hospitalization indicated for other clinical sequelae (eg, renal impairment, pulmonary infiltrates)
 
Grade 4: Life-threatening; pressor or ventilatory support indicated
	
Stop Infusion.
 
Additional appropriate medical therapy may include but is not limited to:
 
 
• Epinephrine**
 
• IV fluids
 
• Antihistamines
 
• NSAIDs
 
• Acetaminophen
 
• Narcotics
 
• Oxygen
 
• Pressors
 
• Corticosteroids
 
 
Increase monitoring of vital signs as medically indicated until the patient is deemed medically stable in the opinion of the Investigator.
 
Hospitalization may be indicated.
 
** In cases of anaphylaxis, epinephrine should be used immediately.
 
Patient is permanently discontinued from further study drug intervention.
	
No subsequent dosing

Abbreviations: CTCAE = Common Terminology Criteria for Adverse Events; IV = intravenous; NCI = National Cancer Institute; NSAIDs = nonsteroidal anti-inflammatory drugs; PO = by mouth

Appropriate resuscitation equipment should be available at the bedside and a physician readily available during the period of drug administration.

For further information, please refer to the Common Terminology Criteria for Adverse Events v5.0 (CTCAE) at <http://ctep.cancer.gov>

